This study was a retrospective, non-interventional, multi-centered, observational study. The study started collecting patients in December 2022 and completed in February 2024. Patients diagnosed with IgA nephropathy of any histology who were treated according to standardized practices according to the KDIGO glomerulonephritis guideline, and who were treated for the first time with finerenone were included. The inclusion criteria were age 18 to 75 years, primary IgAN diagnosed by renal biopsy, receive the highest tolerable dose of RASI inhibitors for at least 3 months, serum potassium <5 mmol/L and protein-to-creatinine ratio (PCR) >0.3 mg/g. The exclusion criteria included secondary IgAN, autosomal dominant polycystic kidney disease or autosomal recessive polycystic kidney disease, lupus nephritis, previous renal transplantation, malignant tumor, active malignancy, heart failure with ejection fraction $<40\%$ and followed up less than 6 months. Patients will also be excluded if they stop taking their medication on their own during the follow-up observation period.

This study was conducted at the Fourth Affiliated Hospital of Zhejiang University School of Medicine, the First Affiliated Hospital of Zhejiang University School of Medicine and Jinhua Municipal Centeral Hospital Medical Group. This study was approved by the Ethics Committees of the Fourth Affiliated Hospital of Zhejiang University School of Medicine.

The primary end point was percentage change in PCR from baseline to 6 months. The

secondary end point contained percentage change in PCR from baseline to 1, 2 and 3 months, frequency of patients with a 30% and 50% decrease in PCR and the level of change in clinical indicators, such as eGFR, serum creatinine, albumin, blood sodium and etc.. The focus of the safety analysis was on serious adverse events, decrease in eGFR of more than 30% and 40% from baseline, and hyperkalemia.

We collected clinical data at months 0, 1, 3, and 6 after the use of the drugs by following up and enquiring about their consultation records. Statistical analysis was performed using SPSS software to analyse and compare the baseline data of the two groups, calculate the changes in UACR, blood potassium, and eGFR in the treatment groups, and compare the differences between the groups. It was considered statistically significant when $p<0.05$.

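### Months 0, 1, 3 and 6 are the only collection times stated, so hyperkalaemia or eGFR falls that arise and resolve between them would be missed if the protocol is followed as written; the size of the loss is unknown

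*Protocol*

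**What the plan says.** All relevant text is in the Protocol, Study design and Methods.

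- **Design:** "This study was a retrospective, non-interventional, multi-centered, observational study".
- **When data were taken:** "We collected clinical data at months 0, 1, 3, and 6 after the use of the drugs".
- **How they were obtained:** the same sentence goes on "by following up and enquiring about their consultation records".
- **Safety outcomes:** "The focus of the safety analysis was on serious adverse events, decrease in eGFR of more than 30% and 40% from baseline, and hyperkalemia".
- **Stated analysis of laboratory values:** "calculate the changes in UACR, blood potassium, and eGFR in the treatment groups", then a comparison between groups.

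The collection sentence speaks of clinical data in general and does not separate efficacy from safety. No other sentence provides for values between the listed months, and none says that such values are set aside.

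**The concern.** Percentage change in PCR is defined at set times, so a fixed grid suits it. Hyperkalaemia and a large fall in eGFR are different: a patient counts as a case if the event happened at all during follow-up, and either event can appear and be corrected between two collection points. The gaps here are 1, 2 and 3 months. As written, a patient with raised potassium in month 4 and normal values at months 3 and 6 would enter the safety table without an event.

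Safety is named in the study title. Patients must be on the highest tolerable dose of a RAS inhibitor and have serum potassium below 5 mmol/L at entry, so potassium is a central question. A reader will take the reported proportions as the share of patients affected over 6 months. If they rest on three looks, any error from missed episodes makes the drug appear safer.

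**Working it through.** The protocol gives no event rate, episode duration or visit window, so there is no planned figure to reproduce. Two checks can be made.

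**1. Direction.** For one patient, let S be the values at months 1, 3 and 6, and A all values in the records from first use to month 6. S is contained in A. If any value in S meets the criterion, so does some value in A; the reverse need not hold. Over a fixed number of patients N:

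(patients with an event in S) / N ≤ (patients with an event in A) / N

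This takes recorded values at face value and needs no assumption about how long episodes last.

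**2. Size, as an illustration only.**

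From the protocol: post-baseline points at months 1, 3 and 6, taken as days 30, 90 and 180.

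Assumed, not in the protocol: one episode per patient, of length d days; onset uniform over 180 days; testing exactly on the three days.

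An episode is seen at day v if it starts between v − d and v. The gaps before the three points are 30, 60 and 90 days, so, without double counting:

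share detected = [min(d, 30) + min(d, 60) + min(d, 90)] / 180

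For d ≤ 30 this is 3d / 180.

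| d (days) | Sum | Uniform onset, exact days | Early onset, exact days | Uniform onset, any value within 14 days |
|---|---|---|---|---|
| 3 | 9/180 | 5% | 4% | 44% |
| 7 | 21/180 | 12% | 11% | 51% |
| 14 | 42/180 | 23% | 25% | 62% |
| 30 | 90/180 | 50% | 72% | 81% |
| 60 | 150/180 | 83% | 97% | 99% |
| 90 | 180/180 | 100% | 100% | 100% |

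The early-onset column is a simulation with exponential onset, mean 30 days, cut off at day 180. In the last column each point catches onsets over d + 28 days, less any overlap and any part outside days 0 to 180. For d = 7 this is 35 + 35 + 21 = 91, and 91/180 = 51%.

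Detection therefore runs from about 4% to 100%. It is governed by duration and window, neither of which the protocol states.

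**The case against.** The strongest reply is that the text does not restrict ascertainment. It never uses the word only, and it names consultation records as the source. A reviewer reading the record for month 3 could see an episode from month 2. The list of months may also be incomplete: a secondary endpoint is "percentage change in PCR from baseline to 1, 2 and 3 months", yet month 2 is not a listed collection point, and those two statements need reconciling in any case. This part stands: a reader might infer that interim values were discarded and that the safety rates are understated as a matter of fact, but the protocol does not say so. The source clause tells how data were obtained, however, and does not widen when. If the text is read as silent, three centres may apply three different rules, and the same correction is needed.

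Other limits also stand:

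- Serious adverse events are not clearly tied to the grid, so the point covers the two laboratory outcomes and not the whole safety objective.
- A patient counted at any of three visits contributes to an interval-sampled cumulative proportion. Calling it a point prevalence would be wrong.
- A reader might conclude that about half to three quarters of episodes are lost. That follows only if episodes are assumed to last 2 to 4 weeks; a sustained eGFR fall would be seen at the next point.
- Fixed times are suitable for the analysis of changes that the protocol does state.
- Counting any value makes the rate depend on how often a patient was tested, which can distort a comparison between groups.

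It can also be said that event rules belong in a statistical analysis plan, and one may exist. That does not dispose of the point: the protocol itself fixes the collection times, and no analysis plan can use values that were never extracted.

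**Conclusion.** The point holds in conditional form. On the ordinary reading, hyperkalaemia and eGFR falls of more than 30% and 40% have three post-baseline looks, and the proportion of patients with an event can only equal or fall below the one obtained from all recorded values. The direction is firm given that reading. The size is not: depending on assumed duration, onset and visit window, the grid could miss nearly all episodes or none. No single percentage should be quoted as the loss.

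A separate problem acts on the same rates whatever the grid. Patients "followed up less than 6 months" are left out, and "Patients will also be excluded if they stop taking their medication on their own during the follow-up observation period". Either exclusion can remove patients with safety events, and the change proposed here does not repair that.

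**What to change.** - Keep months 0, 1, 3 and 6 for PCR, for changes in laboratory values and for any comparison between groups.
- For the descriptive safety rates, also extract every potassium and creatinine/eGFR result and every admission available in the reviewed records, from first finerenone use to month 6.
- Count a patient as having an event if any value meets the study's criterion.
- Report this any-value rate beside the scheduled-visit rate, with the number of tests per patient.
- State the rule in the protocol so that all three centres apply it in the same way.

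The cost is more extraction from records already under review, with no new tests or visits. How much it adds depends on what those records hold between the listed months, which the protocol does not say. The any-value rates can only be the same or less favourable. They will also depend on testing frequency, since patients tested more often have more chances to be counted; that is why both rates and the test counts should be shown together.

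### The protocol defines one cohort with a PCR primary endpoint, but its statistical sentence compares two undefined groups and names UACR where PCR would be expected

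*Protocol*

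**What the plan says.** All the relevant text is in the protocol's Study design and Methods section.

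- **Design:** "This study was a retrospective, non-interventional, multi-centered, observational study". No allocation rule, control or comparator is described.
- **Population:** IgA nephropathy patients "who were treated for the first time with finerenone were included", on background RAS inhibition.
- **Primary endpoint:** "The primary end point was percentage change in PCR from baseline to 6 months". PCR is spelled out in the inclusion criteria as the protein-to-creatinine ratio.
- **Secondary endpoints:** these include "percentage change in PCR from baseline to 1, 2 and 3 months" and "frequency of patients with a 30% and 50% decrease in PCR". They end with an open-ended list of clinical indicators that includes eGFR.
- **Data collection:** "We collected clinical data at months 0, 1, 3, and 6 after the use of the drugs".
- **Statistical methods:** one sentence. It will "analyse and compare the baseline data of the two groups", calculate change in UACR, potassium and eGFR within treatment groups, and test the between-group differences. A second sentence sets significance at p<0.05.

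**The concern.** The population text and the analysis text describe different studies. The first gives one cohort followed before and after starting a drug. The second gives a comparison of two groups, and the reader cannot tell who is in either.

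The design decides what the study can conclude. A single-arm before-after study can report that PCR changed while patients took finerenone. A controlled comparison could address the efficacy question in the title, subject to confounding, but only if the comparator and the start of its follow-up are specified. In a retrospective study, leaving group membership and the urine measure open also leaves room to settle both after results are known.

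The naming of UACR adds a second, smaller problem: the sentence that should carry the primary endpoint into an analysis names another proteinuria measure instead.

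**Working it through.** No arithmetic applies: the protocol states no sample size, effect size, variability or power. The check sets the statements side by side.

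**Step 1. Count the groups.** The inclusion rule defines 1 cohort. The statistical sentence assumes 2 groups, of which 0 are defined. References to two groups or to treatment groups occur only in that sentence.

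**Step 2. Try each meaning the two groups could have.**

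- *Finerenone users against untreated patients.* The second group fails the inclusion rule as written, which admits only first-time finerenone users. Its eligibility and index date are not given.
- *Two subsets of finerenone users.* This satisfies the inclusion rule, but no splitting variable is named. If the mean PCR changes in the subsets are d1 and d2, the between-group test addresses d1 − d2 = 0. That holds for any common value d1 = d2, whether zero or large, so the p-value does not show whether PCR changed on finerenone.
- *The same patients before and after treatment.* One cohort has one baseline, so there would be no two sets of baseline data to compare. The first clause of the sentence rules this out.

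No reading satisfies the inclusion rule, the statistical sentence and the primary endpoint together without adding something the protocol does not contain.

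**Step 3. Match the analysed variables to the endpoints.**

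| Variable in the statistical sentence | Where else it appears |
|---|---|
| eGFR | Named secondary indicator; also a safety item |
| Potassium | Eligibility limit; corresponds to the hyperkalemia safety item |
| UACR | Nowhere else; abbreviation not expanded |

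Two of the three variables match. The third does not. PCR, the primary measure, is absent from the sentence. In its usual meaning UACR measures albumin and PCR total protein, so one is not a synonym for the other, and the protocol nowhere says it treats them as such.

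**Step 4. Ask whether the endpoint itself creates the conflict.** It does not. A per-patient percentage change can serve as the outcome in either a single-arm or a two-group analysis. The conflict lies in the undefined groups and, separately, in the urine measure.

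**The case against.** The strongest reply is that this is one summary sentence, that a separate analysis plan may exist, and that mapping each endpoint to a method is commonly left to such a plan. The primary endpoint is itself well fixed in variable, metric and time. This stands as far as it goes: the absence of PCR from a summary sentence would not by itself be a finding. It does not answer the point here, because the protocol states two things that do not agree. It admits one population and analyses two groups, and it names one urine measure as primary and another in the analysis.

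A second reply is that the secondary list is open-ended, so UACR could fall within it. That is fair. The supportable statement is that no list names UACR, not that it is excluded. UACR may also be a slip for PCR, in which case that part is a wording correction and the undefined groups remain.

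A reader might go further and infer any of four things that the document does not support:

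- *That the study is certainly single-arm, or that a comparator certainly existed.* The inclusion rule points one way; the plural treatment groups and the plural drugs in the data-collection sentence point the other. Either text may be the error.
- *That every PCR endpoint has been separately left without an analysis.* There is one omission in one sentence; counting it once per endpoint inflates it.
- *That the error can be given a size in percentage points of PCR.* The 30% and 50% figures are per-patient response thresholds, not expected mean effects, and no comparator change is given.
- *That any correction is necessarily post hoc because* "The study started collecting patients in December 2022 and completed in February 2024". The document carries a date of 2023-6-1 and does not say when results were seen, which is what matters in a retrospective study.

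**Conclusion.** The point holds as a contradiction within the protocol. One cohort is defined; the only statistical sentence compares two groups that are defined nowhere and that do not fit the inclusion rule if one of them is untreated. The same sentence names UACR where PCR would be expected. Applied literally, a between-group analysis of UACR cannot be run on the defined cohort and does not estimate the primary endpoint.

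The two parts differ in weight. The undefined groups must be resolved, because they determine whether the study is controlled and what it may claim. The UACR label alone would be a wording correction.

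The conclusion rests on the protocol alone. A separate plan could add the method for PCR, but the protocol's own statements would still disagree until reconciled.

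**What to change.** Reconcile the population and analysis text, and state whether the study is single-arm or controlled.

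- **If single-arm:** replace the between-group test with the within-patient percentage change in PCR from month 0 to month 6, with a confidence interval. Limit the conclusion to an observed change in an uncontrolled cohort.
- **If a comparator was intended:** define its eligibility and index date, and compare PCR change between groups adjusted for baseline PCR.
- **In either case:** name PCR in the analysis sentence, or state that UACR is an additional measure. State whether the correction was made before or after results were seen.

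**Cost.** The single-arm route is a text correction, and its price is a weaker claim. It assumes that PCR was recorded at months 0 and 6: the endpoint implies this, but the data-collection sentence says only that clinical data were collected, so it should be confirmed. The comparator route needs record extraction for those patients where it has not been done, an amendment covering them, and an adjusted analysis that would still leave unmeasured confounding.

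### The primary endpoint is percentage change in PCR, but the only analysis sentence names change in UACR, a different and undefined measure

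*Protocol*

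**What the plan says.** All of the relevant text is in the protocol's Study design and Methods section.

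- **Entry criterion.** PCR is spelled out here, its only definition: "protein-to-creatinine ratio (PCR) >0.3 mg/g".
- **Primary endpoint.** "The primary end point was percentage change in PCR from baseline to 6 months".
- **Secondary endpoints.** These include "percentage change in PCR from baseline to 1, 2 and 3 months" and "frequency of patients with a 30% and 50% decrease in PCR", followed by an open list of clinical indicators, "such as eGFR, serum creatinine, albumin, blood sodium and etc".
- **Analysis.** The final paragraph names SPSS, a comparison of baseline data between two groups, and then the instruction to "calculate the changes in UACR, blood potassium, and eGFR in the treatment groups" and compare the groups. The sentence after it gives only the significance threshold, p<0.05.

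**The concern.** A protocol's analysis statement should pick up the variable that its primary endpoint defines. Here the only proteinuria variable named for analysis is UACR, and the primary endpoint is in PCR. I take UACR in its usual sense, urine albumin-to-creatinine ratio; the protocol does not define it. On that reading the numerators differ: albumin in one, total protein in the other. The document neither equates the two nor gives a conversion.

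At stake is what the main result rests on. A percentage change in UACR is not an estimate of the percentage change in PCR, and the counts of patients reaching a 30% or 50% decrease can differ between the two. The study is retrospective and draws on consultation records, so two named measures also leave room to choose between them after the results are known.

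**Working it through.** **Step 1. Set the places side by side.**

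| Place in Study design and Methods | Measure named |
|---|---|
| Inclusion criterion | PCR |
| Primary endpoint, 6 months | PCR |
| Secondary endpoints, months 1, 2 and 3 | PCR |
| Responder endpoints, 30% and 50% | PCR |
| Statistical analysis sentence | UACR |

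PCR is used four times and UACR once. No place names both.

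**Step 2. Match the analysis sentence to the endpoints.** It names three variables. eGFR is a listed secondary indicator and a safety outcome. Blood potassium has a looser counterpart in the hyperkalemia safety outcome. UACR has no named counterpart.

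**Step 3. Test the readings that would remove the conflict.**

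- *Albumin in the secondary list means UACR.* It stands between serum creatinine and blood sodium, so it reads as a blood value.
- *UACR is covered by the open end of that list.* This is possible, but it does not explain why an unlisted indicator is named for analysis while the primary variable is not.
- *The Background mentions albuminuria.* That is a guideline threshold for diabetic nephropathy, not an outcome of this study.
- *UACR is a slip for PCR.* This is plausible, but nothing in the text lets a reader tell a slip from a choice.

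**Step 4. Illustrate how far the measures can part.** The protocol has no figure to reproduce here. It gives no albumin shares, so those below are assumptions. Let f0 and f1 be albumin's share of urine protein at baseline and follow-up. In common units UACR = PCR × f, so for a fractional PCR fall d:

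UACR change = (1 − d) × (f1/f0) − 1

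| Assumed share, f0 to f1 | PCR fall 30% | PCR fall 50% |
|---|---|---|
| 0.70 to 0.60 | UACR −40.0% | UACR −57.1% |
| 0.70 to 0.65 | UACR −35.0% | UACR −53.6% |
| constant | UACR −30.0% | UACR −50.0% |
| 0.65 to 0.70 | UACR −24.6% | UACR −46.2% |
| 0.60 to 0.70 | UACR −18.3% | UACR −41.7% |

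Worked examples: 0.70 × (0.60/0.70) − 1 = −40.0%, and 0.70 × (0.70/0.60) − 1 = −18.3%.

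In the other direction, a patient whose UACR falls by exactly 30% has a PCR change of 0.70/(f1/f0) − 1:

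- share 0.70 to 0.60: 0.70/(0.60/0.70) − 1 = −18.3%
- share 0.60 to 0.70: 0.70/(0.70/0.60) − 1 = −40.0%

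The first patient meets the 30% cut-off on UACR but not on PCR. In the table, a patient with exactly a 30% PCR fall and a share rising from 0.60 to 0.70 meets it on PCR but not on UACR.

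**The case against.** The strongest reply is that the endpoint text is explicit and consistent, and that one word in a later summary sentence should not outweigh it. That sentence is plainly not a full specification: it also omits serum creatinine, albumin, blood sodium, serious adverse events and the responder rates, and its potassium entry matches an endpoint only loosely. The absence of PCR is therefore weak evidence that PCR was not analysed. A statistical analysis plan, not available here, could name the variable for each endpoint. The albumin shares are hypothetical, and nothing in the protocol suggests that only UACR was recorded.

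Much of this stands. The text does not show that PCR went unanalysed, UACR may be a further indicator or a slip, and the illustration shows only that the measures can diverge, not that this study's result would change. The case in which only UACR was recorded is a contingency, not an inference from the text.

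It does not remove the point. The protocol does more than leave the variable to a later plan: it names one, and the one it names differs from its own primary endpoint. A separate analysis plan could add detail, but this text would still contradict itself on the main variable.

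**Conclusion.** The concern holds, and the conflict must be resolved because it touches the primary endpoint. The protocol defines its main result in PCR and states its analysis in UACR, without defining UACR or linking the two. Taken literally, the stated analysis does not produce the stated primary endpoint.

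This conclusion rests on the wording alone, with UACR read in its usual sense. The size of any effect on the results cannot be derived from the document. It is nil if albumin's share of urine protein is constant; under the assumed shifts between 0.60 and 0.70, a 30% PCR fall corresponds to a UACR fall of anywhere from 18% to 40%, and a 50% PCR fall to one of 42% to 57%.

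**What to change.** First confirm which urine measure was recorded at months 0 and 6 at the three hospitals. The protocol says only that clinical data were collected, so it does not settle this. Then use one measure throughout.

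- **If PCR was recorded:** name percentage change in PCR from baseline to month 6 as the primary analysis variable in the analysis sentence. Either delete UACR, or define it and list it as a secondary or supportive outcome. The cost is wording only.
- **If only UACR was recorded at follow-up:** say so openly, and reconcile the primary endpoint, the early-month and responder endpoints, and the PCR entry criterion with it. The cost is a restatement of those items and disclosure of the change, including that it was made in a retrospective study.
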